6.2. Analysis method

Intent to treat analyses

Intent to treat analyses are used to assess whether the intervention resulted in changes in primary and secondary outcomes.

The primary intent to treat analyses uses mixed-effects models.

For continuous outcomes available at only one point in time (Y_{ij} , such as gestational weight gain from the 2nd to the 3rd trimester and length of gestation), we use a linear mixed-effects model with study cluster (u_j) and individual (ε_{ij}) as random effects assuming an exchangeable error structure, and treatment arm (A_j) and covariates (X_{ij} , see below) as fixed effects.

$$Y_{ij} = A_j\beta + X_{ij}\gamma + u_j + \varepsilon_{ij} \quad (1)$$

For continuous outcomes available at multiple points in time (Y_{ijt} , such as dietary intake), we use linear mixed-effects models that use all of the longitudinal data with study cluster (u_j), individual (α_{ij}), and time (ε_{ijt}) as a random effects assuming an exchangeable error structure, and treatment arm (A_j), survey round (T_t), the interaction between study arm and survey round ($A_j \cdot T_t$), and covariates (X_{ijt} , see below) as fixed effects.

$$Y_{ijt} = A_j\beta + X_{ijt}\gamma + T_t\delta + A_j \cdot T_t\theta + u_j + \alpha_{ij} + \varepsilon_{ijt} \quad (2)$$

The same linear mixed models are used for dichotomous outcomes (such as preterm birth and prevalence of emotional violence), but we use robust standard errors to account for heteroscedascity.

For select outcomes assessed at multiple points in time (i.e., emotional violence towards the pregnant woman/mother of the newborn child; controlling behaviors towards the pregnant woman/mother of the newborn child; and physical violence towards the pregnant woman/mother of the newborn child) we assess the impact on the occurrence at any point in time (i.e., at either the 2nd trimester, 3rd trimester, or 2 months postpartum survey) using a model as shown in (1).

Even though randomization should yield equivalence between arms on covariates, we include covariates or make other adjustments (such as re-weighting) in case of non-equivalence of enrollment measures or due to differential attrition. In addition, we include covariates (tentative list in Table 4) that are orthogonal to the randomized treatment assignment and are known or suspected predictors of the outcome of interest (such as, maternal age and education) to reduce residual noise (i.e., increase statistical power). A tentative list of covariates is presented in Table 4. Decisions on which covariates to ultimately include is based on factors such as the extent to which potential covariates are correlated with outcomes, the share of observations with missing values of potential covariates, and the extent to which potential covariates have realistic distributions.

Table 4: Tentative list of covariates to be included in regression models

Outcome	Covariates
All outcomes	Socio-economic status (using census data), upazila, woman's educational attainment, woman's age, season, having an NID
Dietary outcomes	Additional covariates: Interviewer, day of week
Prevalence of emotional violence, controlling behaviors, physical violence, stress	Additional covariates: partner's age, partner's educational attainment, woman's gestational age
Attachment	Additional covariates: -
Birth outcomes	Additional covariates: Maternal height, maternal BMI at census, primiparity, child sex
Household food security, value of household consumption	Household adult equivalents

Distributional assumptions for outcome variables is checked using descriptive statistics. Transformations are used for continuous outcome variables if needed to obtain more symmetric distributions.

In addition to the models described above, we conduct robustness checks by estimating fixed effects models.

The intent to treat analyses do not include any subgroup analyses (e.g., by maternal age, season, etc.)

Modified intent to treat analysis

Based on field reports, a considerable proportion of women who are eligible for MCBP and included in our study may not have enrolled in MCBP. Consequently, if the addition of top-up cash or food has effects on the study outcomes over and above the base MCBP, these effects may not be detected in the intent to treat analysis, as the impact in those enrolled is diluted by the absence of impact in those not in the program. If we find that enrollment in the program is indeed low, we will consider conducting modified intent to treat analysis, to assess if the program had an impact within the subgroup who enrolled. The exact method used depends on patterns in the data.

It is possible that some of the difference in enrollment across arms could be explained by differences in observables across arms, but we do not yet know. If there appears to be selection bias in enrollment that differs by treatment arm, we will use quasi-experimental analytical methods. For example, inclusion of additional covariates, propensity score methods, or matching methods may be appropriate if women's observable pre-pregnancy characteristics measured in the census appear to predict well whether they enroll; if the distributions of these observable characteristics show meaningful overlap across arms; and if empirical patterns do not suggest a strong role for unobserved factors that both predict enrollment and differ systematically by arm.

Exploratory analysis

Exploratory analyses are conducted to assess the heterogeneity of impact, i.e. to evaluate whether the impact was different in specific subgroups (such as women in more vs. less disadvantaged households, women with lower vs. higher levels of education, women of younger vs. older age, women who co-reside with mothers-in-law vs. women who do not co-reside with mothers-in-law at 2nd trimester) or by season. To assess the heterogeneity of impact, we stratify the analyses on the possible effect modifier. The analyses are considered exploratory as they are not adequately powered.

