3.1. Trial design

A three-arm cluster-randomized, non-blinded, community-based, mixed cross-sectional and longitudinal trial is used to estimate the effectiveness of the intervention. The unit of randomization is a grouping of 3 wards³. Each ward group is randomly assigned to one of three study groups, all of which receive the improved maternity allowance program:

- **Arm 1 – “standard” package, i.e., base cash and nutrition behavior change communication (BCC):** pregnant women receive 800 BDT each month and group-based BCC on nutrition with a focus on how to improve their dietary intake during pregnancy.
- **Arm 2 – “standard” package + food basket:** pregnant women in this arm receive the base cash of 800 BDT each month, group-based BCC, and in addition a monthly food basket composed of rice, lentils, and oil valued at approximately 1,000 BDT.
- **Arm 3 – “standard” package + top-up cash:** pregnant women in this arm receive the base cash of 800 BDT each month, group-based BCC, and in addition receive a monthly additional cash transfer of 1,000 BDT instead of the food basket.

The study is a hybrid of a cross-sectional and longitudinal design. It follows women from their second trimester of pregnancy to around 2 months after childbirth. A census is conducted to identify households with women who met the program’s eligibility criteria (see Section 5.2). The study then uses a total of 6 three-month long data collection waves. Women in the 2nd trimester of pregnancy (based on self-reported last menstrual period⁴ and ultrasound reports and antenatal care cards when available) were enrolled in the study in the first four waves (Figure 1). Household and individual data are collected at enrollment. In the wave following enrollment, data are collected on the same women who are now in the 3rd trimester. Third trimester data collection is conducted at around 34 weeks of gestation (± 1 week). Subsequent waves are used to assess newborn weight and length (collected within 72 hours after child birth) and to assess anthropometric and other outcomes at around 2 months postpartum (61 days ± 1 week). In the final follow-up round (1 month in length), women in the 3rd trimester of pregnancy not captured in wave 5 are surveyed. In addition, the newborn survey is conducted. The number of survey rounds is based on the sample size calculations presented below and field reports regarding the actual number of study subjects enrolled and successfully followed up.

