³ The administrative structure in Bangladesh consists of divisions (8), districts (64), subdistricts or upazilas (491), and unions. Up to about 15 years ago, each union consisted of 3 wards. Since then, the ward system was changed to 9 wards per union, each identified by a number (i.e., from 1 to 9). The study uses the old definition of wards (i.e., 3 per union) as the unit of randomization.

⁴ Pregnancy trimesters are defined as follows: 1st trimester: 2 to 13 weeks of pregnancy (meaning, weeks since first day of the last menstrual period); 2nd trimester: 14 to 26 weeks of pregnancy; 3rd trimester: 27 weeks of pregnancy until delivery.

[figure not shown]

Figure 1: Study design (note: dates are approximate)

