- **Mean probability of micronutrient adequacy:** the mean of the probabilities of adequacy for 11 key micronutrients (iron, calcium, zinc, vitamin A, thiamin, riboflavin, niacin, vitamin B-6, vitamin B-12, vitamin C, and folate) is calculated using the 24hr recall data. Given continued advances in this field, the final analytic strategy to calculate the adequacy for each nutrient is based on recommended best practice at the time of the analyses. For now, we anticipate using the methods as used by Nguyen and colleagues (Nguyen et al., 2018); and the WHO's estimated average requirements (EAR) to calculate the probability of adequacy for each micronutrient (World Health Organization, 2004; World Health Organization & Food and Agriculture Organization of the United Nations, 2004). Usual intakes are estimated using the data from a second 24hr recall collected on a non-consecutive day for a subsample of pregnant women. A power transformation is used to obtain symmetrical distributions for each nutrient; and a measurement-error model is applied to adjust for the within person variance of nutrient intake (34,52). The estimated usual intake is used to calculate the probability that the usual intake was above the EAR during pregnancy (53). Impact is assessed in the 2nd and 3rd trimester.
- **Length of gestation:** The difference between the date of birth and the first day of the last menstrual period (assessed in the first survey) is used to calculate length of gestation (days).
- **Preterm birth:** Using the length of gestation, we determine the proportion of children born before 37 weeks (or 259 days) of gestation.

- **Prevalence of emotional violence towards the pregnant woman/mother of the newborn child:** Prevalence of any emotional intimate partner violence in the past 6 months measured using the WHO Violence Against Women instrument (54). Impact is assessed in the 2nd and 3rd trimester of pregnancy and at 2 months (i.e., 61 days) postpartum.
- **Prevalence of controlling behaviors towards the pregnant woman/mother of the newborn child:** Prevalence of any controlling behaviors in the past 6 months measured using the WHO Violence Against Women instrument (54). Impact is assessed in the 2nd and 3rd trimester of pregnancy and at 2 months (i.e., 61 days) postpartum.

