- **Prevalence of physical violence towards the pregnant woman/mother of the newborn child:** Prevalence of any physical intimate partner violence in the past 6 months, measured using the WHO Violence Against Women instrument (54). Impact is assessed in the 2nd and 3rd trimester of pregnancy and at 2 months (i.e., 61 days) postpartum.
- **Stress of the pregnant woman/mother of the newborn child:** Measured using women's Perceived Stress Scale score (55). Impact is assessed in the 2nd and 3rd trimester of pregnancy and at 2 months postpartum.
- **Maternal-fetal attachment:** Maternal attachment to their unborn child is assessed during their 3rd trimester of pregnancy using the Prenatal Attachment Inventory (56). In the Bangla translation of the Prenatal Attachment Inventory, all items in the scale were rephrased as questions instead of statements to make it easier for the interviewer to ask and to enhance the respondents' understanding.
- **Maternal-infant attachment:** Maternal attachment to their infant is assessed at 2 months (i.e., 61 days) postpartum using the Postpartum Bonding Questionnaire (57). The items in the Bangla-version of the scale were rephrased as questions instead of statements to simplify the interview process. Additionally, 2 of the 25 items in the original scale were removed. These 2 items (i.e., "I have done harmful things to my baby" and "I feel like hurting my baby") made up the subscale on Risk of Abuse and had low sensitivity (57). The sum of all items on the full scale, as well as each of the three subscales (Bonding, mother-infant relationship, and infant-focused anxiety), is used as outcome indicators.
- **Husband/partner of the pregnant woman:**
 - **Stress of the husband of the pregnant woman:** Measured using men's Perceived Stress Scale score (55). The second- and third-trimester assessment is used to assess impact.
- **Infant**
 - **Birthweight:** Birthweight (grams) is assessed within 72 hours after delivery to avoid the influence of transitory neonatal weight loss that typically happens during the first days of life.
 - **Low birthweight:** Low birthweight is defined as a birth weight below 2500 grams.
- **Household**

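### The any-time violence outcome counts the 2nd-trimester survey, whose six-month recall adds mainly pre-programme time, so this added analysis is likely attenuated (minor)

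*SAP*

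**What the plan says.** The three violence measures are primary outcomes with a six-month recall (SAP section 6.1): "Prevalence of any emotional intimate partner violence in the past 6 months", "Prevalence of any controlling behaviors in the past 6 months" and "Prevalence of any physical intimate partner violence in the past 6 months". Section 6.1 defines impact round by round: "Impact is assessed in the 2nd and 3rd trimester of pregnancy and at 2 months (i.e., 61 days) postpartum". Model (2) in section 6.2 delivers this through "the interaction between study arm and survey round". The detectable differences in section 3.3 are also given by round.

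Section 6.2 then adds, for these three measures only, a single-time-point model for "occurrence at any point in time (i.e., at either the 2nd trimester, 3rd trimester, or 2 months postpartum survey". No detectable difference is given for it, and nothing says how to read it beside the round-specific results.

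On timing, section 3.1 has "2nd trimester: 14 to 26 weeks of pregnancy" (footnote 4) and "Third trimester data collection is conducted at around 34 weeks of gestation", within one week either way. The last survey is 61 days after birth, give or take a week. Eligibility requires pregnancy (section 5.2), and adherence allows a woman to seek programme enrolment as late as the 4th month (section 4.2).

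**The concern.** A six-month recall taken at 14-26 weeks of pregnancy reaches back to conception or before it. Later surveys cover the rest of pregnancy, so what the 2nd-trimester survey brings to the composite is largely violence that occurred before a woman could have received anything from the programme. Such reports occur at the same rate in every arm. They turn women positive regardless of what the programme does afterwards, and so shrink the arm difference.

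At stake is interpretation. The any-time model stands under the intent-to-treat heading and concerns primary outcomes. A null result could be reported as no effect on violence when part of the explanation is the recall window.

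**Working it through.** **The plan's own figures.** Section 3.3 gives detectable reductions in pregnancy of 7, 7 and 6 points from prevalences of 40.0%, 79.5% and 19.9%. Inputs: 24 women per cluster, 48 clusters per arm, intra-cluster correlation 0.01, cluster-size CV 0.424, covariate correlation 0.1, two-sided 5%, power 90%. The design effect is 1 + ((1 + 0.424²) × 24 − 1) × 0.01 = 1.273. With one cluster taken off the 48, the solution is 7.36, 6.51 and 5.75 points, which round to the plan's values. They are round-specific; there is none to reproduce for the any-time outcome.

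**Recall windows**, in weeks from the LMP, taking six months as 26 weeks:

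- 2nd trimester, interview at week g (14 to 26): opens at g − 26, that is −12 to 0.
- 3rd trimester, interview at 33-35: opens at 7-9.
- Postpartum, birth assumed at 39.5-40 weeks: opens at about 21-24.

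The last two overlap. The 2nd-trimester survey therefore adds only the time from g − 26 to the opening of the 3rd-trimester recall. This is 7-21 weeks, mean 14.

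**Share of the added time before exposure.** At g = 20 the added time is weeks −6 to 8, or 14 weeks. Before the LMP: 6/14 = 43%. Before entry at week 4: 10/14 = 71%. Before entry at week 8: 14/14. Averaged over uniform interview timings, the shares are 43%, 71% and 98%, and 100% for entry at weeks 13 and 17.

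**What this does to the contrast: one case by hand.** Emotional violence, entry at week 8, mean timings (20, 34 and 48.5 weeks), gamma frailty with shape 1. Assume the programme lowers the hazard proportionally, so that a fully exposed 26-week window falls from 40% to 33%.

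- Weekly hazards: (1/0.60 − 1)/26 = 0.02564 before entry or in the control arm; (1/0.67 − 1)/26 = 0.01894 after entry. Risk = 1 − 1/(1 + H), where H is the cumulative hazard.
- Two later surveys, weeks 8 to 48.5: H = 1.038 v 0.767; risk 50.9% v 43.4%; difference 7.5 points.
- All three, weeks −6 to 48.5: H = 1.397 v 14 × 0.02564 + 0.767 = 1.126; risk 58.3% v 53.0%; difference 5.3 points.
- With 1,152/1.273 = 905 effective women per arm, the standard error is about 0.0234 and 0.0233. Power is Φ(3.22 − 1.96) = 90% and Φ(2.28 − 1.96) = 63%.

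**Range.** The same model was run over frailty shapes 0.3 to 3 and random timings, now charging the two-survey version for its losses. The three-survey version uses all 1,286 enrolled per arm. The two-survey version uses 1,152, a quarter of them classified on the 3rd-trimester survey alone (section 3.3 expects about a quarter without the 61-day visit). Power, two-survey v three-survey:

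| Entry | Emotional | Controlling | Physical |
|---|---|---|---|
| Week 4 | 84-92% v 59-79% | 89-91% v 59-62% | 94-97% v 79-93% |
| Weeks 8-17 | 54-91% v 25-68% | 53-90% v 22-50% | 69-97% v 38-86% |

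At a given entry week and frailty, the net loss is 12-25, 28-32 and 5-16 points at week 4, and 23-36, 31-45 and 12-33 points at weeks 8-17. The low two-survey values come from late entry, which leaves 19% (week 13) to 35% (week 17) of the 3rd-trimester recall unexposed. If exposure began at the LMP itself, the loss would be only 4-14, 16-17 and 0-6 points.

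**The case against.** **The any-time model is an extra.** The outcomes are defined and powered by round, and model (2) tests each round. In the same illustration the 3rd-trimester round alone has about 87%, 94% and 93% power for entry at week 4. This stands. A reader might infer that the primary violence results are biased or that the trial cannot detect an effect on violence. The documents do not support that: randomisation keeps the any-time comparison valid, and the 3rd-trimester and postpartum estimates do not use the earlier recall.

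**The power loss depends on how the programme works.** If it prevents only new onset, the absolute difference does not shrink. With differences held at 7, 7 and 6 points and 1,152 per arm, adding the 2nd-trimester survey leaves emotional violence at 85-86% power, slightly raises controlling behaviours, and costs physical violence about 4-6 points. The SAP does not say which mechanism is expected. This stands.

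**Full enrolment is optimistic.** Section 6.2 itself warns that a considerable share of study women may never enrol. With 50% enrolled (an assumption), neither any-time version exceeds 47% power. For emotional violence at week 17 the net loss falls from 27-29 points to 8-9. This stands.

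**Dropping the survey trades dilution for selection.** About 10% of enrolled women, mostly those with fetal loss, would leave the composite, against the aim in section 4.3 to use all available data. This argues against replacing the three-survey version. It does not argue against reporting a second one, which conditions on follow-up no more than the planned 3rd-trimester and postpartum estimates do.

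**Conclusion.** The timing point is secure, because it follows from the SAP's own survey windows and recall period. For women seen in all rounds, the 2nd-trimester survey adds only time before about week 7-9, and for entry at week 4 or later most of that is pre-programme. Attenuation of the any-time contrast is likely. Its size is not established: roughly 5-45 points of net power under full enrolment, entry at weeks 4-17 and a proportional reduction in hazard. It is less if exposure starts at the LMP or many women never enrol, and possibly nil on the absolute scale if only new onset is prevented. Quoting one figure as the loss, or calling the three-survey outcome invalid, would go beyond the documents. The severity is minor: an added analysis lacks a companion definition and a reading rule.

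**What to change.** In section 6.2, pre-specify a second any-time outcome for the three violence measures: a report at the 3rd-trimester or the 2-month postpartum survey, with women who have only one of these classified on that one. Report it beside the three-survey version, which keeps all women. State that the time contributed by the 2nd-trimester survey is mainly pre-programme, so a null three-survey result alone is not to be read as no effect. Report by arm how many women have neither later survey.

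The cost is wording only, since the surveys already provide the data. The downside is that the two-survey version omits about 134 of 1,286 women per arm (10%; 1,286 − 1,152, section 3.3) and so conditions on later follow-up. The resulting shift is about the arm difference in loss times the difference in violence prevalence between lost and retained women: 0.02 × 0.20 = 0.4 points, or 0.05 × 0.20 = 1.0 point. In the illustration the dilution removed is 1.6-2.5 points (emotional), 1.8-3.0 (controlling) and 0.7-2.0 (physical). Strong selection could therefore cancel the gain for physical violence, which is a further reason to show both versions.

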6.3. Missing data

Approaches for handling missing data depend on the outcome or covariate.

For instances when a limited amount of information is missing that is needed to construct an outcome variable (e.g., the price of a consumed food which is needed to construct total household expenditure), we impute the missing information using single imputation drawing on the non-missing data.

When outcomes (such as birthweight) or covariates are missing, decisions on whether and how to impute missing values is based on assessing patterns in the data, such as the share of missing values, the expected reason for missing values, and whether there is sufficient other information to impute missing values well. Outcomes assessed at multiple times that are missing are not imputed because the mixed model handles these missing values assuming that they are missing at random.

If an outcome has a large share of missing values, robustness checks may be conducted to assess if impact estimates may suffer from selection bias. This may include comparing the characteristics of households or individuals for which the outcome is missing with those for whom the outcome is not missing and the calculation of Lee Bounds.

